RESPONSE: Aim 1: Determine the safety and feasibility of externally mounted magnetic devices for extended (> 1 week) home use for the management of early post-acute and chronic eyelid movement disorders. Aim 2: Collect preliminary data on the efficacy of external magnetic eye lid devices stemming from a variety of different pathologies.

OBJECTIVES

3) Your focused research question needs to be further refined into one or more study objectives. The study objective(s) should be single and quantifiable statement(s) that will allow you to answer your research question.

RESPONSE: Objective 1: Determine the safety and feasibility of externally mounted magnets for extended management of chronic eyelid movement disorders by measuring visual acuity and corneal and skin integrity and comfort over 8 weeks of wear.

HYPOTHESES

4a). Primary Hypothesis - Hypotheses are more specific than objectives and amenable to statistical evaluation. Your primary hypothesis is your statement of the hypothesized effect on the primary outcome measure. A hypothesis is worded very simply and written as 'testable' statements. Your experimental results will prove or disprove your hypothesis. Hypotheses are generally stated in the null form (H_0) as they have their basis in inferential statistics. Rejecting the null hypothesis increases our confidence, with a given level of probability, that there is a relationship between the variables being studied. However, a classic scientific hypothesis includes both a null and alternative (H_a) hypothesis.

**e.g. H_0 : Asthma prevalence rates are not different among children from low and high socioeconomic groups in Istanbul. H_a : Asthma prevalence rates are different among children from low and high socioeconomic groups in Istanbul.*

RESPONSE: Hypothesis: Externally mounted magnet systems will have a good safety profile defined as a mean decrease in visual acuity 1 line or less, high-mag photo documented skin-integrity rating better

than 2 (FDA industry scale), and no more than a two grade (NEI/Industry Workshop scale (Lemp, 1995)) worsening in superficial punctate keratitis on high mag photo-documented analysis.

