spectacle mounted magnet may also be used for lagophthalmos (mounted within the inferior eye-wire to pull the upper lid down). In this scenario there is no lower lid array. **20 MINUTE TRIAL:** For both the ptosis and lagophthalmos magnet devices: If experimenter likert-type scale score is greater than or equal to 6 on the blink mechanics and efficacy and better than 8 on the skin integrity and the participant rated comfort is greater than or equal to 5/10 on likert-type or 50mm or better on a 100mm Visual Analog Scale and they express a desire to continue wearing the device, they will be offered participation in an extended 20 minute trial. This is followed by a repeat of the visual acuity, slit lamp exam, video and rating scale data collection. **EXTENDED 1-WEEK TRIAL:** Participants who have a successful 20 minute magnet device trial defined as an Examiner Rating Scale score of greater than or equal to 6 on the blink mechanics and efficacy, better than 8 on the skin integrity, participant rated comfort greater than or equal to 5/10 (or 50mm on a 100mm Visual Analog Scale), and express a desire to continue wearing the device will be offered participation in an extended 1-week trial. These cut-offs were based on observations during the pilot study at Spaulding (see manuscript attached) where patients who reported a desire to wear the device typically rated their comfort and satisfaction at this level or better. The PI or other trained study staff supervised by the PI will train the patient how to apply and remove the lid magnet; similar to what is done for insertion removal of contact lenses. They will be trained how to place on the secondary magnet spectacles to sit in the correct position on their face. If the participant is able to successfully demonstrate the ability to do this, only then will the magnet device be dispensed home with the patient (see exception* below). During each 1-week during the extended trial, the participant will be advised (instructional sheet sent with the participant) to wear the device as much as they would like up to 8 hours per day in the case of ptosis and 24 hours per day for lagophthalmos so long as comfort remains 5 or better (see participant instructions). Participants will be asked to document their wear time and assess their comfort on a 10-pt scale (10 being best) on a regular (min. daily) basis. For lagophthalmos, the device ideally will be worn 24 hours/day. For ptosis, the magnet glasses will be removed at night, and the lid magnet will remain attached to the eyelid. The participant may shower/wash face with the lid magnet on as the Tegaderm is not critically bothered by water and the magnet is encased in PDMS. They will be advised not to submerge the device (i.e. swim with the device on). Lid magnets will be removed and applied as they start to become detached (typically 2-3 days). If self-assessed comfort is worse than 5/10 or if the intervention fails (eg. stops working or falls off and cannot be reapplied) the participant will be instructed to contact the PI directly. The PI will advise if the device should be removed, and will come to MEEI or Schepens within 24 hours of the complication to evaluate the problem. If there is a problem requiring immediate attention, the participant will be advised to seek attention in the MEEI EW. **AT A 1-WEEK FOLLOW-UP** study appointment we will repeat visual acuity, slit lamp, rating instruments and video recording. **SAFETY CUTOFFS:** The participant's study status will change to suspended and an adverse event reported to the IRB with any of the following findings at the follow-up or any emergency visit: Any broken skin, decrease in visual acuity more than 2 lines, worsening of corneal rating of more than 1.5 points or other ocular surface ratings more than 2 points, and comfort rating lower than 5/10 (or 50cm on the 100cm visual analog scale). The extended trial of the magnet device may be renewed 3 times (for a total of 1 month with weekly visits) as long as the above mentioned criteria continue to be met. If still safe/effective at 1 month, the participant will be given the option to take the device home for an additional 1 month. The device trial/study ends after 8-weeks (4 weekly trials followed by a 1-month trial) or with failure/complication or voluntary withdrawal. If the device is successful over the duration of the study and the participant would like to continue wearing it, a clinical decision will be made as to if and for how long per day it should be worn. This is justified when there appears to be no other equivalent treatments which may be substituted. It would not be ethical to retract the device from a participant if it is working and there is no other comparable option. In such cases, the participant will return 1 month later for an additional follow-up evaluation prior to turning the maintenance of their care over to the neuro-ophthalmology, oculoplastics, or vision rehabilitation service. Their specialist will continue to monitor for complications after the study if the patient keeps the device. The study will end when 25 participants in each group have completed the study (~2yrs). **EXCEPTION* TO TRAINING REQUIREMENT:** If the participant is unable to apply and remove the device themselves (physical or cognitive limitations) and/or they have cognitive impairment (MMSE 20-23), they may still participate in an extended 1-week trial if the following criteria are met: 1) a caregiver is able to be trained to apply/remove the device, 2) The primary caregiver assures 24-hour supervision (see form on the last page of the "instructions for use document"), 3) The cognitively impaired participant (or participant who cannot apply the device themselves) agrees to attend daily study visits for the first

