groups to which they were originally randomly assigned (despite withdrawal, treatment failure or cross-over). Consultation with a statistician is strongly recommended. [See Harvard Catalyst Statistical Consulting for more information.](#)

RESPONSE: Descriptive statistics will be calculated including a mean rating scale value for skin, corneal integrity, and visual acuity (logmar). A repeated-measures ANOVA will be used to determine if there is any change across visits/measurements. The completeness of opening and closing with and without the magnet and with the other devices will be compared using paired t-tests. As this is not a randomized design, ITT will not be used.

DATA SAFETY MONITORING PLAN (DSMP)

Complete question 15 **OR** 16 depending on the risk of the study. If your study is submitted as minimal risk and determined by the HSC to be more than minimal risk you will be asked to complete question 16 during the review process.

15) If the research is **no more than minimal risk**, please describe any provisions in place to ensure the safety of participants and the validity and integrity of data. If safety monitoring will occur a safety monitoring plan may include elements such as: parameters for safety review, the frequency in which safety review will occur, the person(s) responsible for safety review, and the plan (including the person(s) responsible) for reporting adverse events, protocol deviations, or noncompliance to the HSC and others (where applicable). Data monitoring may include the specific elements that will be reviewed (e.g., informed consent documentation, verification of the accuracy of data), the frequency of data monitoring, and the person(s) responsible.

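### Suspension rules remove later visits because of the safety outcome, the repeated-measures ANOVA has no rule for this, and the safety proportion has no stated denominator

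*Combined protocol and SAP*

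**What the plan says.** - **Analysis (Section 14).** "Descriptive statistics will be calculated including a mean rating scale value for skin, corneal integrity, and visual acuity (logmar". Then: "A repeated-measures ANOVA will be used to determine if there is any change across visits/measurements". The only statement on who is analysed is "As this is not a randomized design, ITT will not be used". No other set is named, and nothing is said about missed visits or visits after suspension.
- **Suspension (Section 8, safety cut-offs).** The participant's "study status will change to suspended and an adverse event reported to the IRB with any of the following findings": broken skin, acuity loss of more than 2 lines, corneal worsening of more than 1.5 points, other ocular-surface worsening of more than 2 points, or comfort below 5/10. These are "findings at the follow-up or any emergency visit".
- **Continuation (Section 8).** Weekly renewal is allowed "as long as the above mentioned criteria continue to be met". Also: "The device trial/study ends after 8-weeks (4 weekly trials followed by a 1-month trial) or with failure/complication or voluntary withdrawal".
- **Criterion (Section 4a).** Good safety includes "a mean decrease in visual acuity 1 line or less", with no visit or population named, together with limits on skin rating and keratitis.
- **Event count and proportion (Sections 7a and 13).** Section 7a defines an adverse event by the same thresholds, allows suspension to be temporary or permanent, and sets no visit limit. Section 13 makes the proportion of participants with a safety issue, and of those completing, the primary report. It does not say whether the base is those consented, fitted, sent home or completing.
- **Numbers (Section 8).** One sentence enrols 25 per group; another ends the study once 25 per group have completed.

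**The concern.** Whether a participant is still under observation depends on the values being analysed. For acuity and cornea, the trigger and the analysed variable are the same measurement. For skin they share a construct: the trigger is broken skin, while the analysis averages a rating. Comfort is a trigger but is not in Section 14's list of means.

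The reading that triggers suspension is recorded; the visits after it are lost. A repeated-measures ANOVA in its usual complete-case form discards the whole participant. A later-visit mean omits that participant unless the suspension is lifted. Both pull the results towards safety. Not being randomized is a reason not to call the set ITT, but it does not remove the need to define one.

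Two results are at stake. The mean acuity part of Section 4a could read as met partly because those who worsened have left. The safety proportion, which answers Aim 1, changes with a denominator that the plan leaves open.

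**Working it through.** The plan gives no figure to reproduce here: Section 13 declines a power calculation for the primary outcome, and no SD or breach rate is stated.

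**1. Effect on the mean.** From the plan: 25 per group; visits at weeks 1, 2, 3, 4 and 8; suspension above 2 lines; limit of 1 line. Assumed: all 25 are dispensed the device; person i has a true week-8 loss L_i ~ N(mu, SD); the reading at week w is L_i x g(w) + error, with error SD 0.5 line; suspension is on acuity only and permanent; the suspension reading is kept. There were 20,000 simulated trials. Completers are those with a week-8 reading, including anyone whose first breach is at week 8.

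| Case | mu, SD, g(w) | Left before week 8 | First breach at week 8 | Completer mean | Limit met, completers | Limit met, all followed |
|---|---|---|---|---|---|---|
| a | 1.5, 2, w/8 | 15.2% | 25.8% | 1.00 | 49.7% | 10.9% |
| b | 1.5, 1, w/8 | 4.9% | 28.7% | 1.43 | 2.7% | 1.3% |
| c | 1.5, 1, min(w/2, 1) | 47.3% | 3.4% | 0.79 | 81.2% | 1.3% |
| d | 0.5, 1, w/8 | 0.9% | 8.5% | 0.48 | 99.0% | 98.7% |

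The last column can be checked directly. The standard error is sqrt(SD^2 + 0.5^2)/sqrt(25).
- (a): sqrt(4.25)/5 = 0.412, and Phi(-0.5/0.412) = 11%.
- (b) and (c): sqrt(1.25)/5 = 0.224, and Phi(-0.5/0.224) = 1.3%.
- (d): Phi(0.5/0.224) = 98.7%.

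When completers meet the limit, the mean number of breaches among the 25 is 9.0 in (a) and 12.4 in (c).

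Other inputs give intermediate results. With linear loss, SD 1.5 and error SD 1, a true 1.5 lines reads as 1.07. For the cornea (cut-off 1.5 points), a true worsening of 1.0 point reads as 0.97 (SD 0.5, error SD 0.5) to 0.76 (SD 1, error SD 0.75), with 94% to 73% of participants having all visits.

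**2. Alternatives on the same data, cases (a), (b), (c); truth 1.5.**

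| Summary | a | b | c |
|---|---|---|---|
| Mixed model, suspension reading kept | 1.51 | 1.50 | 1.50 |
| Mixed model, suspension reading left out | 0.89 | 1.08 | 0.96 |
| Last recorded reading | 1.21 | 1.47 | 1.62 |

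With the reading kept, the model meets the limit in 11.6%, 1.5% and 6.5% of trials. In (d) it gives 0.50, met in 98.7%. Keeping the suspension reading is what makes it work.

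The model has a limit. Suppose people also stop for other reasons that track their underlying loss (logit probability at a visit of -2.5 + (loss - mu)/SD, so that 37%, 34% and 56% are lost in all). The model then gives 1.21, 1.28 and 1.44, against completers' 0.66, 1.16 and 0.73 and last readings of 0.77, 0.99 and 1.48.

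**3. Denominator.** Exact 95% limits are the Beta quantiles B(0.025; x, n-x+1) and B(0.975; x+1, n-x). Take an assumed 4 breaches:
- 4/25 fitted = 16% (4.5-36.1%)
- 4/20 dispensed = 20% (5.7-43.7%)
- 4/15 dispensed = 27% (7.8-55.1%)

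**4. Enrolled versus completed.** With an assumed loss of 10%, 20% or 30%, 25 enrolled leave 25 x 0.9 = 22.5, 25 x 0.8 = 20 or 25 x 0.7 = 17.5 completers. To have 25 completers needs 25/0.9, 25/0.8 or 25/0.7, which round up to 28, 32 or 36 enrolled per group. If completers became the base, suspended participants could fall out of it.

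**The case against.** **Harm is not hidden.** A reader might infer that the plan conceals safety failures. It does not: every breach goes to the IRB and is counted as an adverse event, and Section 13 already makes the safety proportion primary. This stands. The result would be contradictory, not concealed.

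**The plan does not specify a complete-case or week-8 completer mean.** This also stands. Complete-case ANOVA is the usual default, not plan text; the ANOVA tests change, not the 1-line limit; and Section 4a also requires the skin and keratitis limits, so acuity alone cannot satisfy it. The percentages in the table hold only for one reading of a criterion that the plan leaves open. That openness still needs closing.

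**The large effects need severe inputs.** True. Case (a) implies that 1 - Phi(0.25) = 40% of people truly lose more than 2 lines and Phi(-0.75) = 23% gain; case (c) has nearly half suspended before week 8. The simulation also treats suspension as permanent, although Section 7a allows it to be temporary. In (b) and (d) the effect on meeting the limit is under 2 percentage points.

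**People never sent home cannot breach.** This tempting inference is not supported. Section 8 ties the cut-offs to follow-up or emergency visits, but Section 7a does not, and the 20-minute trial repeats acuity, slit lamp and comfort ratings. The numerator is therefore ambiguous as well as the denominator.

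**A mixed model is elaborate for a descriptive single-arm study.** Partly fair: it will be imprecise at 25 per group. But the plan already names an inferential test across visits, and the substitute uses the same data without discarding suspended participants.

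**Conclusion.** The concern holds. Visits go missing because of the safety outcome, and neither the ANOVA nor the means come with a rule for it. The bias runs towards safety. Its size cannot be known from the plan: it is negligible with mild loss, or with slow loss and modest variation, and it reaches a completer mean of about 0.8-1.0 line for a true 1.5-line loss when loss is early or varies widely. All SDs, loss patterns and breach counts are assumptions, as is reading Section 4a as a week-8 completer mean.

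The denominator gap needs no simulation: it follows from the text, as do the difference in scope between Sections 7a and 8 and the conflict between enrolling 25 and completing 25. This should be fixed before analysis. It does not show that the plan hides harm or that the acuity criterion would be wrongly met.

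**What to change.** 1. **Safety proportion (Section 13).** Aim 1 concerns home use, so make the main result the proportion with any breach among all participants dispensed the device, including those suspended or withdrawn, by group with an exact 95% CI. Show the all-fitted proportion beside it; as the main figure it could dilute the home-use rate. Report completion separately. Reconcile Sections 7a and 8 on whether breaches during fitting and the 20-minute trial count. Reconcile the two statements on 25 per group so that completers do not become the base.
2. **Change over visits (Section 14).** Replace the repeated-measures ANOVA with a linear mixed model of change from baseline in all dispensed participants, with visit as a category and the suspension reading kept. Set a visit-window rule that gives one reading per window and uses the suspension reading where there is one. The rule should cover the daily first-week visits under the training exception and ties such as week 6, which is two weeks from both week 4 and week 8. Take the Section 4a mean acuity result from this model at a named visit.
3. **Sensitivity.** Add one summary using each person's last recorded reading, and state that the model does not cover every form of informative stopping.

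The cost is wording plus a standard model on data already collected, with no extra visits and no change to the suspension rules. Reported means may be less favourable, the model is imprecise at 25 per group, and the exact interval is wide: even 0/25 has an upper limit of 13.7%.

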4b). Secondary Hypotheses - Although a study is usually based around a primary hypothesis, secondary hypotheses may also be pre-specified although based on outcomes of lesser importance or additional interest. As the primary hypothesis is usually the basis for statistical power calculations, secondary hypotheses with insufficient power will generally not lead to statistically robust conclusions.

RESPONSE: Externally mounted magnet systems will a) result in a significant improvement in the completeness of eye closure and opening as measured using image analysis of eye opening/closing with compared to without the device; b) will be comfortable to wear defined as a mean participant-reported comfort rating greater than or equal to 6/10 (or 60cm on a 100cm visual analog scale)

STUDY DESIGN

5) State the design of the research (e.g. randomized controlled study, cross-sectional survey, prospective or retrospective cohort/case-control).

**Whatever the study design, you need to ensure that you provide the reader with a clear statement and description of your proposed design. You may also explain why the particular study design has been chosen in preference to other possible designs (i.e. justification for choice of study design)*

RESPONSE: This is a prospective study. As the principal aim of this study is to determine safety and feasibility of extended home use, we will not attempt to randomize patients to a treatment and a placebo group nor will we have an age-matched control group. Participants will be made aware that a predicate device is commercially available and the magnet device is experimental.

ELIGIBILITY CRITERIA

6a). Inclusion Criteria - Inclusion criteria are the 'characteristics' that clearly describe the study population that are required for a subject to be included in the study. The criteria may be based on factors such as age, gender, the type and stage of a disease, previous treatment history, and co-morbid medical conditions. They may state appropriate criteria for admitting special 'at-risk' populations such as women of reproductive age, children or patients with disease states or organ impairment.

RESPONSE: Presence of an eyelid movement disorder for at least one eye, moderate cognitive function or better defined as greater than or equal to 18 out of 30 on a pre-screening of the Mini-Mental State Exam, age 5 or older

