RESPONSE: Skin integrity scales, change in ocular surface staining rating, participant comfort and satisfaction rating, and change in visual acuity. Skin integrity will be analyzed by applying a likert-type rating system to a high-mag/high-resolution photo documented image of the subject's lid skin. The number of adverse events will also be reported, defined as incidents which require temporary or permanent suspension of the participant's involvement. These include any broken skin, decrease in visual acuity more than 2 lines, worsening of corneal rating of more than 1.5 points or other ocular surface ratings more than 2 points, and comfort rating lower than 5/10 (or 50cm on the 100cm visual analog scale).

7b). Secondary Outcome(s) - Secondary outcome(s) are measures of additional or less important research interest. They may include additional clinical, psychological, economic, or safety outcomes (e.g. treatment related side effects/adverse events). However, as these endpoints are not used to calculate study power and sample size it is often not possible to draw robust conclusions from the results.

RESPONSE: Video analysis of eyelid biomechanics to measure the completeness of eye closure and opening compared to 1) no device, 2) relative to the contralateral side (if normal), 3) relative to the ptosis crutch or external lid weights. The same paired comparisons will be performed for the clinician and participant rating scale data. 3) Cognitive score on the MoCA will be analyzed for relationship to length of time in the study and satisfaction rating scores).

STUDY PROCEDURES

8) In this section you need to clearly and comprehensively describe exactly what will happen to participants once they are enrolled in your study. Depending on the study it might include how potential participants will be approached, when they will be randomized, the frequency and duration of visits or whether they are expected to self-complete a daily diary at home, the duration of the study or follow-up, and any measurements taken at each visit (e.g. questionnaires, physical measurements, biological samples).

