13) Sample size and statistical power - A sample size or power calculation should be performed. This calculation is used to estimate the number of subjects required to answer your primary study hypothesis with an accepted power. Conversely, it also allows you to estimate what power can be achieved with a limited number of participants. This number is calculated by specifying the magnitude of the effects that are expected (i.e. informed and clinically significant), variability of the measurements and the acceptable degree of type I and II errors. You need to specify the assumptions made for the calculation. It is recommended that you consult with a statistician for this section. Also keep in mind the estimated recruitment rate and whether you need to adjust for anticipated non-responders and losses to follow up.

RESPONSE: The primary hypothesis is that externally mounted magnet systems will have a good safety profile and will be feasible for home use therefore we will report the proportion of participants who have a safety issue and complete the trial. As this outcome is based on summary statistics and not comparisons between groups, a power calculation is not appropriate. Sample size was selected based on providing an as-broad-as-possible but feasible (within the time of the study) assessment of safety and feasibility. The sample size calculation for the secondary within subject comparison between devices is estimated at 10 for the ptosis group, using preliminary unpublished data for cranial nerve III palsy at Spaulding (n=7; efficacy for opening (mm) magnet vs. crutch was borderline with 7 participants p=0.08, and comfort had reached significance, p=0.05). A power calculation is not possible for the lagophthalmos group as preliminary data are only available for 3 participants. Power calculations for the secondary analysis will be re-evaluated during data collection.

14) Statistical methods - The statistical methods used for the study objectives/hypotheses (e.g. t-test, chi-squared, multivariate modeling) must be sufficiently detailed. If conducting a randomized controlled study, you should state whether methods will include an “intention to treat” (ITT) analysis, per protocol analysis, or both. An ITT analysis is preferred as it compares all subjects in the

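### The only inferential test planned for the safety measures asks whether anything changed, not whether change stays within the stated limits, and no confidence interval is planned

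*Combined protocol and SAP*

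**What the plan says.** Section 4a (primary hypothesis) states limits, not absence of change: "good safety profile defined as a mean decrease in visual acuity 1 line or less", a "high-mag photo documented skin-integrity rating better" than 2, and "no more than a two grade (NEI/Industry Workshop scale (Lemp, 1995)) worsening in superficial punctate keratitis". Only the acuity limit is expressly a mean. For skin and keratitis the text does not say whether the limit applies to a mean or to each participant. Section 4b(b) adds a second mean limit: "comfortable to wear defined as a mean participant-reported comfort rating greater than or equal to 6/10".

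Section 14 plans descriptive means for skin, cornea and acuity, then the analysis quoted as "A repeated-measures ANOVA will be used to determine if there is any change across visits/measurements". Its paired t-tests concern lid opening and closing, a secondary outcome. Section 7b extends paired comparisons between devices to the rating scales.

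Section 13 says of the primary hypothesis that "we will report the proportion of participants who have a safety issue and complete the trial". It calls this summary statistics and gives no power calculation for it. Section 7a also reports the number of adverse events, using individual cutoffs that include "decrease in visual acuity more than 2 lines, worsening of corneal rating of more than 1.5 points".

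No section gives a confidence interval, an acceptable rate, or a rule that links a mean or proportion to a limit.

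**The concern.** A hypothesis that harm stays within a limit needs an estimate and its uncertainty, set against that limit. The repeated-measures ANOVA answers another question. A significant result may reflect a small loss well inside the limit, or even an improvement, since the overall F-test has no direction. A non-significant result may mean only that the sample is small or the readings noisy. The planned paired comparisons also test for zero difference, so they do not address the 6/10 comfort limit either.

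What bears on the limits is the reported means and proportions, and these are planned without any measure of precision. The background section describes this as the first study to send participants home with the device. A safety conclusion drawn from an ANOVA p-value, or from a bare mean just under 1 line, could therefore carry more weight than the data allow.

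**Working it through.** **The plan's own figure.** There is none for the safety hypothesis. The only calculated sample size, 10 in Section 13, belongs to the secondary device comparison in ptosis. It can be reached from the pilot comfort result (n=7, p=0.05). Taking p as two-sided, t = 2.447 on 6 df, so the standardised difference is 2.447/√7 = 0.925, and (1.960 + 0.842)²/0.925² = 9.2, rounded up to 10. Alpha of 5% and power of 80% are assumed. This has no bearing on the limits.

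**Inputs.** From the documents: limit of 1 line (4a); 25 per group, 50 in all (Section 8); acuity readings at baseline, weeks 1–4 and week 8 (Section 8). Assumed, because the documents give nothing: SD of within-person acuity change of 1–2 lines, normal changes, a linear decline, independent reading errors, and 15 participants as an example of a group reduced by withdrawals.

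**ANOVA against the limit.** With k = 6 readings and SD of change 1.5, the within-person variance is 1.5²/2 = 1.125. The noncentrality is λ = n × Σ(mean at visit − overall mean)² / 1.125, on 5 and 5(n−1) df. Two spacings are shown: equally spaced readings, and the actual weeks 0, 1, 2, 3, 4, 8.

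| Final loss | n | Σ (equal; actual) | λ | Result |
|---|---|---|---|---|
| 0.5 line | 25 | 0.175; 0.156 | 3.89; 3.47 | significant in 27%; 24% |
| 0.5 line | 50 | 0.175; 0.156 | 7.78; 6.94 | significant in 54%; 49% |
| 1 line | 15 | 0.700; 0.625 | 9.33; 8.33 | not significant in 40%; 45% |

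Simulations of the same set-up gave 24–28%, 49–55% and 40–47%, so those ranges are used. Other SDs show the mismatch in both directions. At n=25, a 0.8-line loss (inside the limit) with SD 1 is significant in about 96% of simulated runs, and a 1.2-line loss (outside it) with SD 3 is non-significant in about 64%.

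**Observed mean alone, n=25.** P(observed mean ≤ 1 line) = Φ((1 − true loss)/(SD/√25)). For a true loss of 1.25 lines:
- SD 1: Φ(−0.25/0.20) = 11%
- SD 1.5: Φ(−0.25/0.30) = 20%
- SD 2: Φ(−0.25/0.40) = 27%

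**One-sided 95% upper limit, n=25.** The limit is met if observed mean + 1.711 × SD/√25 ≤ 1. Pass probabilities come from the noncentral t.

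| SD | Largest passing mean loss | True 0 | True 0.5 | True 1.25 |
|---|---|---|---|---|
| 1 | 1 − 0.342 = 0.66 | 99.9% | 78% | 0.2% |
| 1.5 | 1 − 0.513 = 0.49 | 94% | 49% | 0.7% |
| 2 | 1 − 0.684 = 0.32 | 78% | 33% | 1.2% |

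Pooling all 50, a true 0.5-line loss passes 97%, 75% and 54% of the time for SD 1, 1.5 and 2.

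**Proportions.** With no events in n participants the exact one-sided 95% upper limit is 1 − 0.05^(1/n): 11.3% for 0/25 and 5.8% for 0/50.

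**The case against.** The strongest reply is that this is an uncontrolled feasibility study whose Section 13 disclaims formal inference for the primary hypothesis and names its own analysis: the proportions with a safety issue and completing. Section 7a adds the adverse-event count. On that view a binding confidence rule imports a confirmatory test that the study was not sized for. Much of this stands. The cost is real: a true loss of 0.5 line, comfortably inside the limit, would pass only 33–78% of the time at n=25.

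Three stronger readings are tempting, and the documents do not support them.

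- A reader might infer that the plan offers nothing that bears on the hypothesis. The acuity limit is itself a mean, so the reported mean can be compared with it directly. What is missing is its precision.
- A reader might infer that a mean could hide large individual losses: 5 of 25 participants losing five lines averages 5 × 5/25 = 1 line. Each of those five exceeds the 2-line cutoff in Section 7a, and would be counted as an adverse event and suspended under Section 8.
- A reader might infer that a device at the limit is wrongly called safe half the time. A true mean loss of exactly 1 line satisfies Section 4a as written. With SD 1–2 lines, it would also put about 16–31% of participants beyond 2 lines, roughly 4 to 8 of 25, and these would be reported alongside the mean.

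The reply does not close the gap. Section 13 does not define a safety issue and gives no acceptable rate or interval. The Section 7a cutoffs are not the Section 4a limits, so the event count answers a related but different question. And Section 4a does set numeric limits for its safety claim, which calls for some statement of precision.

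**Conclusion.** The concern holds in a limited form. The one inferential test that Section 14 plans for the safety measures does not address the limits in 4a, and no planned test addresses the comfort limit in 4b(b). Means and proportions that do bear on safety are planned, but only as descriptions without precision. With an assumed SD of change of 1.5 lines, the ANOVA is significant for a harmless 0.5-line loss in about 24–28% of cases at n=25 and 49–55% at n=50, and it misses a 1-line loss in about 40–47% at n=15. For a true mean loss of 1.25 lines, the observed mean at n=25 falls within the limit 11–27% of the time (SD 1–2 lines).

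The mismatch between test and hypothesis can be read from the text and needs no assumption. Its size depends on the assumed SDs and the linear decline, because the documents give no SD. This does not invalidate the study; it limits how firmly the primary conclusion can be stated.

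**What to change.** In Section 14:

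1. Report the mean acuity change from pre-device baseline and the mean comfort rating with confidence intervals. Name the visit at which each is judged, whether by group or pooled, and how participants who stopped earlier are counted.
2. State that the acuity limit (4a) or the comfort limit (4b(b)) is met only if the one-sided 95% confidence limit lies on the acceptable side. Otherwise report the result as inconclusive, not as evidence of harm.
3. Define a safety issue for Section 13. Report the proportions with a safety issue, completing, and losing more than 2 lines, with exact confidence intervals.
4. Label the repeated-measures ANOVA as a description of the time course.

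In Section 4a, state whether the skin and keratitis limits apply to means or to each participant. Reconcile them with the differing cutoffs in Section 7a; which values are right is for the investigator.

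No new data, visits or participants are needed. The cost is a harder claim: at n=25 and SD 1.5 lines the observed mean loss must be about 0.49 line or less, and a true 0.5-line loss passes only about half the time. An inconclusive result is therefore a real possibility, and the protocol should say so in advance.
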